2.1 Primary Objective

- To assess the preliminary efficacy of neoadjuvant BYL719 in patients with transorally-resectable, HPV+ HNSCC, as measured by quantitative change in tumor size (ΔT) following 10-21 days of treatment.
- To evaluate the relationship between genomic *PIK3CA* activation to ΔT

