3.1 Characteristics

This is a single-arm, open label phase II window trial to assess the effect of the PI3K inhibitor, BYL719 on tumor proliferation, size, and biomarker expression following 10-21 days (max 28 days for unexpected delays in planned surgery) of BYL719 monotherapy in patients with operable, HPV-associated oropharyngeal squamous cell carcinoma.

The study design involves baseline tumor biopsy, collection of peripheral blood, and tumor size assessment via CT scan or MRI. After 10-21 days, CT scan or MRI and peripheral blood collection will be repeated, followed by planned oncologic surgery with collection of post-treatment tumor specimen.

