6.2.4 Day 9-29 (inclusive of day of surgery)

During treatment, pre-surgical

Ideally, subjects will have the surgery on day 22 or later. All efforts should be made to schedule these evaluations on **the day prior to or the day of surgery**, however a 5-day window is provided for logistical purposes, except for subjects with surgery on day 11 through 14. Subjects with scheduled surgery on day 11 through 14 should not have these procedures earlier than day 9. Subjects will continue to take BYL719 until the day prior to planned surgery. The interval

between the last dose of BYL719 and surgery will be approximately 24 hours (+/- 8 hours).

Compliance as evidenced by pill count and patient drug diary will be assessed when the subjects return the bottles and any leftover pills. This may happen after their surgery at the first follow-up visit if they do not have a clinic visit the day before surgery.

- *History and Physical Examination (During treatment, Pre-operative):* Subjects will be evaluated by history and physical examination by the treating physician prior to planned surgery (including vital signs, weight, performance status). This visit will also include adverse event assessment and compliance assessment as evidenced by pill count and patient drug diary. For logistical convenience, this visit may be scheduled in conjunction with blood collection and imaging as specified below.

NOTE: If surgery is unexpectedly delayed, subjects will continue to take BYL719, and this pre-operative history and physical examination does not need to be repeated.

- *Clinical and Research Blood Collection:* Subjects will undergo clinical labs including
 - CBC with differential,
 - serum chemistries including fasting glucose,
 - LFTs, and
 - coagulation studies prior to planned surgery.

Research blood will be drawn simultaneously with these standard pre-operative labs.

NOTE: If surgery is delayed, subjects will continue to take BYL719 and the clinical blood tests do not need to be repeated, but the research blood may be redrawn if the delay causes the research blood draw to be outside of the 5-day window prior to surgery.

- *Cross-sectional Imaging for Tumor Measurements (Research):* Subjects will undergo a repeat diagnostic CT scan of the neck with contrast prior to planned surgery as a part of the study. For patients with severe allergy to iodinated contrast dye despite premedication, or in the case of physician preference, neck MRI may be substituted.

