6.3 Surgery and Post-treatment Tumor Tissue Collection

6.3.1 Days 11-22 (window of +7 days up to day 29, inclusive of day of surgery)

- Oncologic head and neck cancer surgery
 - After 10-21 days of neoadjuvant treatment (+ 7 days if required for logistical and scheduling purposes), the patient will undergo the planned oncologic head and neck cancer surgery. The nature of complete resection of the primary head and neck

tumor, type of reconstruction, and levels of nodes to be dissected will be determined by the treating surgeon.

- Prior to surgery, standard of care dental evaluation is recommended, to allow for any necessary dental extractions to be planned in conjunction with surgery. Consultations with a Nutritionist and Speech and Language Pathologist are strongly recommended prior to surgery and as ongoing support post-operatively. Placement of a nasogastric (eg. Dobhoff) or gastrostomy feeding tube is at the discretion of the subject and the study physicians.
- Intraoperative tumor tissue for biomarkers (post-treatment tumor tissue collection)
 - Part of the tumor and/or lymph node specimen will be sent to the research laboratory for mandatory biomarker analyses.
 - If surgery is unexpectedly cancelled and the primary tumor or lymph node is accessible for in-office biopsy in the judgment of the surgeon-investigator, a tumor biopsy may be substituted for the intraoperative specimen.

Tissue collection procedures are described in Section 9.0.

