6.4.3 Other visits

Additional non-protocol visits may occur during the 12-week post-operative period as deemed clinically necessary. Patients will be referred for adjuvant chemotherapy and radiation per standard of care, based upon pathologic findings.

Once the first 12 weeks of follow-up have been completed, study follow-up will be discontinued, and subjects will continue standard treatment and surveillance in accordance with national guidelines.

The standard post-operative visit which occurs 12 weeks post-op (+/- 4 weeks) will be considered the “final study visit.”

Table 6.1 Schedule of Study Procedures and Assessments/Study Calendar

Study Procedures	Baseline	Days 1 through 21	Days 22 through 28 (if surgery is delayed) ^k	Day of Surgery	4-Week Post-op Visit	Final Study Visit (12-week post-op) ^l
Informed consent	X					
History & physical examination ^a	X	To be performed between days 9 through 21			X	X
Vital signs, weight	X	To be performed between days 9 through 21			X	X
ECOG-PS	X	To be performed between days 9 through 21			X	X
Pregnancy test ^b	X					
EKG ^c	X					
Clinical blood tests ^d	X	To be performed between days 9 through 21			X	X
Cross-sectional imaging study ^e	X	To be performed between days 9 through 21				
MUGA or echocardiogram ^f	X					
p16 status	X					
Adverse Event Assessment		At each subject visit during treatment.			X	
Concomitant Medication Assessment	X	At each subject visit during treatment.				
Fasting plasma glucose	X	Every 7 days (+/- 3 days) while on BYL719	X			
Pill count/diary review		Diary review to be done at each visit. Pill count to be done when subject returns bottles and any extra pills.				
BYL719 ^g		Take medication Days 1 through 21	Continue BYL719 if surgery is delayed			
Surgery ^h		Surgery is to be performed day 11 or later.	Surgery may be performed day 22 through day 29.			
Research blood collection ⁱ	X	Complete within 5 days prior to surgery				

Biopsy for Research ^j	X			X		
----------------------------------	---	--	--	---	--	--

- a. History and physical examination within 8 weeks prior to study entry. This should include surgical assessment of the primary tumor, including fiberoptic nasopharyngoscopy or examination under anesthesia as indicated per standard of care, and as determined by the treating surgeon.

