NOTE: Because this is a pre-operative window study with only brief exposure to study drug, and RECIST responses are not anticipated, target lesions will be measured bi-dimensionally and recorded quantitatively. Quantitative change in the RECIST-defined baseline sum diameter (longest diameter of tumor + short axis diameter of up to three pathologic lymph nodes), expressed as a percent, will be the primary endpoint and will be correlated with biomarker modulation.

All tumor measurements pre- and post-treatment will be performed independently by a single neuroradiologist.

Evaluable for quantitative change in tumor size

Only those patients who have measurable disease present at baseline, have received at least 10 doses of BYL719, and have had their disease re-evaluated will be considered evaluable for change in tumor size.

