10.1 Study Endpoints

This is a phase II open label study to identify baseline and/or pharmacodynamics biomarkers of clinical response to BYL719 based on quantitative change in tumor size following 10-21 days of neoadjuvant BYL719 in patients with operable HNSCC. Δ Tumor size will be treated as a continuous variable, based upon the percent change in RECIST-determined index lesions pre and post-treatment.

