10.2 Determination of Sample Size and Accrual Rate

10.2.1 Sample Size and Power Estimate

The primary objective of the study is to identify baseline and/or pharmacodynamic biomarkers that might have predictive utility to determine the clinical response to BYL719. The overall sample size is 14 evaluable patients. Accrual will continue until 14 evaluable patients have enrolled. If patient had baseline tissue samples obtained, has taken at least 10 doses of drug, and has undergone response assessment that is of sufficient quality to assess the primary clinical and biomarker endpoints, they are evaluable. Based upon prior window trials, up to 20 patients will be enrolled to meet these criteria. The sample size is based upon the following considerations: half of enrolled patients will demonstrate genomic PI3K pathway activation, defined as PIK3CA mutation or amplification, or PTEN deletion. We expect those with genetically activated PI3K to demonstrate a median Δ Tumor size of (-)20%, whereas those with no genomic PI3K activation to demonstrate a median increase of (+)5%. Alpha is set to 0.03 and beta is set to 0.20.

As a biomarker study, the statistical design is to accrue a sufficient number of patients and provide 80% power to test one or any of 5 key hypotheses with individual alphas of 0.03: 1) relationship between Δ Tumor size and baseline genomic *PIK3CA* activation; 2) relationship between Δ Tumor size and change in expression of HPV mRNA (qPCR); 3) relationship between Δ Tumor size and change in expression of E6, E7 oncoprotein (immunoblotting); 4) relationship between Δ Tumor size and change in expression of phospho-HER3 (immunoblotting and RPPA); 5) relationship between Δ Tumor size and change in expression of HER3/PI3K dimers (Monogram). 14 patients with complete biomarker data are needed to achieve 80% power for the 5 primary hypothesis and limit overall family wise error rate (FWER) to 15%. Based upon prior window trials, accounting for treatment compliance and quality paired tumor specimens, this will require enrollment of 20 patients.

As an example, to justify the sample size for the first key hypothesis (relationship between Δ Tumor size and baseline genomic *PIK3CA* activation), the standard deviation of Δ Tumor size

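### The post-treatment scan is allowed from day 9, short of the plan's own 10-day minimum, and the 10-dose evaluability rule does not say the doses must come before the measurement

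*Combined protocol and SAP*

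**What the plan says.** **Exposure before the measurement.** The primary objective (section 2.1) is change in tumor size "following 10-21 days of treatment". Section 10.1 repeats it as "quantitative change in tumor size following 10-21 days of neoadjuvant BYL719". Section 3.1 attaches the interval to the scan: "After 10-21 days, CT scan or MRI and peripheral blood collection will be repeated", with surgery to follow.

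**When the scan may be done.** Section 6.2.4 prefers the pre-surgical procedures, including the research CT or MRI, on the day before or the day of surgery, and gives a 5-day window for logistics. For early surgery it sets a floor: "Subjects with scheduled surgery on day 11 through 14 should not have these procedures earlier than day 9". The imaging row of Table 6.1 reads "To be performed between days 9 through 21".

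**When surgery takes place.** Section 6.3.1 uses the same interval for the operation: "After 10-21 days of neoadjuvant treatment (+ 7 days if required for logistical and scheduling purposes), the patient will undergo the planned" surgery. Footnote h to Table 6.1 schedules surgery on days 11-22, with a slip of up to 7 days.

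**Who is evaluable.** Section 7 counts patients with measurable baseline disease who "have received at least 10 doses of BYL719, and have had their disease re-evaluated". Section 10.2.1 words its condition as follows: "taken at least 10 doses of drug, and has undergone response assessment that is of sufficient quality to assess the primary clinical and biomarker endpoints". Section 10.2.2 asks for assessments at baseline and at the end of the window, and gives no dose count at the scan.

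**The concern.** One interval of 10-21 days is attached to two events, the scan and the operation, which section 6.2.4 allows to fall on different days. For early surgery, the scan that supplies the primary endpoint can come before the minimum exposure named in the endpoint's definition. The 10-dose rule looks like the safeguard, but as written it can be met with doses taken after the scan. What is at stake is the meaning of the primary measurement for some of the 14 patients, and who is counted among them.

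**Working it through.** **Inputs.** Day 1 is the first dose (Table 6.1, footnote g). Dosing is once daily and the last dose is on the day before surgery (section 6.2.2). The earliest scan is day 9 for surgery on days 11-14, and otherwise 5 days before surgery (section 6.2.4). Imaging may share a visit with the blood draw (section 6.2.4), and on those days the dose waits until after the draw (section 4.2, Appendix 4). No passage orders dose and scan, so both orders are shown.

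**Formulas.** Let m be the doses missed before the scan.
- Doses by surgery on day s: s − 1 − m.
- Doses by a scan on day d: d − 1 − m if the scan comes first, d − m if that day's dose comes first.

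**The plan's own figure.** With m = 0, surgery on day 11 gives 10 doses and surgery on day 22 gives 21. This reproduces 10-21 days, counted to surgery.

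**Doses at the earliest permitted scan, m = 0.**

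| Scheduled surgery day | Earliest scan day | Doses at scan | Doses by surgery |
|---|---|---|---|
| 11 | 9 | 8-9 | 10 |
| 12 | 9 | 8-9 | 11 |
| 13 | 9 | 8-9 | 12 |
| 14 | 9 | 8-9 | 13 |
| 15 | 10 | 9-10 | 14 |
| 16 | 11 | 10-11 | 15 |
| 22 | 17 | 16-17 | 21 |

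A day-9 scan is short in either order, yet every row reaches 10 doses by surgery and so can satisfy the written dose condition. A day-10 scan is short (9 doses) only if it precedes that day's dose. This can happen with surgery on day 15 at the 5-day limit, or with surgery on day 11 and the scan on the preferred day before. With surgery on day 16 or later and no missed dose there is no shortfall.

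**Missed or held doses.** With m = 1, a day-9 scan follows 7-8 doses, and surgery on day 12 still gives 12 − 1 − 1 = 10. With m = 2, a day-9 scan follows 6-7 doses, and surgery on day 13 gives 13 − 1 − 2 = 10. A slip has the same effect. Suppose surgery is planned for day 11, the scan is on day 9 and two doses were missed: that is 8 doses by day 11, but 10 if surgery moves to day 13. Section 6.2.4 does not require the scan to be repeated. The documents give no rate of missed doses.

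**Power, for context.** The plan uses a two-sample t test with n = 7 per group, difference 25 points, SD 8 and alpha 0.03. The noncentrality is 25 / (8 × √(2/7)) = 5.85 on 12 degrees of freedom. Two-sided power is 0.999, which agrees with the stated figure above 90%. As an assumption only, cutting the whole 25-point difference by 10%, 20% or 30% gives 0.994, 0.978 or 0.934.

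**The case against.** The strongest reply has four parts.

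- **The day-9 sentence is a restriction.** The 5-day window alone would allow scans on days 6, 7 and 8 for surgery on days 11, 12 and 13, and the sentence removes them. Section 6.2.4 also prefers surgery on day 22 or later. This stands, and it makes the problem smaller. But these are preferences, while the day-9 scan is expressly permitted.
- **The 10-21 days may simply label the treatment window up to surgery.** Sections 3.4, 5.1 and 6.3.1 use it so, and sections 2.1 and 10.1 can be read that way. Section 3.1 cannot, because it puts the scan itself after 10-21 days.
- **The evaluability rules list baseline, doses and re-assessment in chronological order.** That is a natural reading, under which a day-9 scan would not qualify. It is not stated, and with 14 evaluable patients the rule should not rest on inference.
- **The endpoint counts days, the evaluability rule counts doses.** A day-10 scan before that day's dose is short only on the dose count. This is fair, and it makes that case weaker than the day-9 case, which is short on both.

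Section 1.2 also expects steady-state plasma levels at 2 to 3 days, so a day-9 scan is well past that point. The documents do not say how tumor change depends on duration, so this limits the concern without settling it.

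**Conclusion.** The mismatch is real and minor. Sections 6.2.4 and Table 6.1 permit the primary measurement before the exposure that section 3.1 requires, and the evaluability rules do not exclude such a patient. With no missed doses, the shortfall is 1-2 doses at a day-9 scan (surgery on days 11-14) and 1 dose at a day-10 scan taken before that day's dose. It is larger if doses were missed or held before the scan.

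Three stronger readings are tempting, and the documents do not support them.

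- **That a large share of patients is affected.** The number of exposed calendar days in the surgery window is not a proportion of patients, and the stated preference is for late surgery. No frequency is given.
- **That the primary result or its power is compromised.** On the plan's own inputs, power stays above 90% even if the whole difference shrinks by 30%. The effect on tumor change cannot be computed.
- **That the interval between scan and surgical tissue after a delay is an error.** Not repeating the scan is a permissive scheduling choice, and section 6.3.1 and footnote h describe a slip of up to 7 days. Reporting that interval would be useful, but nothing in the plan is contradicted.

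**What to change.** 1. In sections 7 and 10.2.1, state that the minimum of 10 doses must have been taken before the post-treatment tumor measurement. Naming the measurement, and not only the scan, also covers the caliper substitute in section 6.2.4.
2. Reconcile the day-9 allowance in section 6.2.4 and Table 6.1 with sections 2.1, 3.1 and 10.1, so that one stated exposure applies to the measurement. How to align the schedule is for the sponsor to decide, as is whether to repeat a scan after a slip.
3. Optionally, list each patient's doses at scan and scan-to-tissue interval in the report.

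**Cost.** The change is to wording. The diary in Appendix 4 already records dose dates and times. Under the clarified rule and with no missed dose, the earliest qualifying scan is day 10 after that day's dose, or day 11. Surgery on day 11 therefore stays feasible, with slightly tighter scan scheduling for early surgery. An occasional patient may need replacing within the ceiling of 20, possibly including one already counted as evaluable. That is not free in a study whose accrual period has been extended from 24 to 64 months.

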6.2.2 Study Drug Treatment - Days 1-21 and 22 (+/- 3 days)

NOTE: BYL719 treatment is planned for 10-21 days, however, may be administered up to 28 days if required for logistical/scheduling purposes.

- BYL719 will be administered at 350 mg orally once daily. This is one 200 mg tablet and three 50 mg tablets.
- The last dose of BYL719 will be taken on the day prior to surgical resection. The interval between the last dose of BYL719 and surgery will be approximately 24 hours (+/- 8 hours).
- If surgery is delayed, BYL719 may be continued until the day prior to surgery, for a maximum of 28 days. If this is the case, additional drug may be dispensed at Day 22.
- Subjects will be asked to indicate on a drug diary (see [Appendix 6](#)) when doses of BYL719 are taken in order to monitor for compliance. Subjects may also use the drug diary for notations on side effects and other treatment related events.

6.2.3 Day 8, 15, and 22 (+/- 3 days) if patient is on BYL719 treatment

- Weekly fasting plasma glucose
- Adverse event assessment.
- Concomitant medication review.

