- b. Pre-menopausal women of child-bearing potential (WOCBP) must have a negative serum pregnancy test within 4 weeks of registration. A negative pregnancy test, serum or urine, must then be documented within 72 hours of Day 1 of BYL719 treatment.
- c. The standard of care EKG performed for pre-surgical evaluation should be used. EKGs performed within 12 weeks prior to study entry may be substituted, provided the patient has experienced no interval cardiac event.
- d. Clinical blood tests will be repeated once within 5 days prior to surgery, and at the 4 week and 12-week post-operative visits if clinically indicated according to the investigator. Blood tests include, CBC with differential, serum chemistries including fasting glucose, LFTs, coagulation studies, except **coagulation studies are not required at the 4 week or 12 week post-surgical visits**. Amylase, lipase, and HbA1c are done at baseline.
- e. Within 6 weeks of study entry (within 4 weeks preferred), and again within 5 days prior to planned surgery, patients will undergo cross-sectional radiological evaluation using diagnostic contrasted CT, PET/CT (with diagnostic contrasted CT), or MRI of regions with radiologically or clinically identifiable tumor.
- f. Cardiac imaging will be performed by Multiple Gated acquisition (MUGA) scan or Echocardiogram (ECHO) in order to assess the left ventricular ejection fraction (LVEF). MUGA or ECHO performed within 365 days prior to study entry may be substituted provided the patient has experienced no interval cardiac event.
- g. The first day of BYL719 treatment will be considered Day 1. BYL719 will be administered at 350 mg daily, for 10-21 days, and will be discontinued on the day prior to surgical resection. If surgery is delayed, the study drug may be continued until surgery, for a maximum of 28 days.
- h. Surgery will be scheduled during days 11-22 of BYL719 treatment. For logistical reasons, surgery may be delayed by up to 7 days (day 29). Postoperative complications, hospital days, and ICU days will be noted for each patient.
- i. Research blood samples will be obtained at baseline (prior to study drug administration, within 3 weeks of registration) and within the 5 days prior to scheduled surgery.
- j. Research biopsies will be obtained at baseline (prior to study drug administration, within 3 weeks of registration) and during planned surgery for resection of the tumor.

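### When surgery slips after the pre-operative draw, repeat CBC, chemistries, LFTs and coagulation studies are waived while BYL719 continues, so results can be up to 12 days old at surgery

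*Combined protocol and SAP*

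**What the plan says.** Footnote d of Table 6.1 sets the on-treatment panel: "Clinical blood tests will be repeated once within 5 days prior to surgery". Section 6.2.4 lists its content (CBC with differential, serum chemistries including fasting glucose, LFTs, coagulation studies). It asks that the pre-operative evaluations be done the day before or the day of surgery, and adds that "a 5-day window is provided for logistical purposes". For surgery on Days 11-14 they should not be done before Day 9.

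Footnote h places surgery on Days 11-22 and allows a slip of up to 7 days, to Day 29. Dosing continues to the day before surgery, for at most 28 doses.

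For a delay, the blood-collection NOTE in Section 6.2.4 says "subjects will continue to take BYL719 and the clinical blood tests do not need to be repeated", but also that "research blood may be redrawn if the delay causes the research blood draw to be outside of the 5-day window prior to surgery". Footnote k, attached to the Days 22-28 column, carries the same waiver and extends it to history and examination, vitals, ECOG status and imaging.

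What stays on the schedule is in Section 6.2.3: "Weekly fasting plasma glucose", adverse event assessment and medication review around Days 8, 15 and 22. Section 6.2.2 foresees the extension, since "additional drug may be dispensed at Day 22".

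**The concern.** Table 5 makes dosing depend on values that only the waived panel measures. Grade 3-4 neutropenia or thrombocytopenia means omitting the dose. Creatinine above 3 x ULN, or AST/ALT above 3 x ULN with bilirubin above 2 x ULN, means permanent discontinuation. Once the draw has been taken and surgery slips, the patient keeps taking drug and no scheduled test can trigger those rows for a new, asymptomatic change. Coagulation studies, which bear directly on fitness for surgery, are waived too.

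The NOTE is also uneven. It recognises that a delay can leave a sample outside the 5 days and offers a remedy for the research sample, while the clinical sample, normally drawn at the same time, is released. At stake is a potentially curative operation going ahead, under the protocol minimum, on results older than the protocol's own interval.

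The scope is narrow: only patients whose surgery moves after the draw. A patient booked from the outset for a date after Day 22 is drawn within 5 days of that date under footnote d.

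**Working it through.** **Inputs.** Planned surgery day S = 11 to 22 (footnote h). Draw day D from max(9, S − 5) to S (Section 6.2.4, footnote d). Slip d = 1 to 7 days (footnote h). Last dose on the day before surgery (Section 6.2.2). On clinic days the dose follows the blood draw (Appendix 4).

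**The plan's own limit.** Latest surgery = 22 + 7 = Day 29. Last dose is on Day 28, so 28 doses. This matches footnotes h and k. The documents state no age for the results.

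**Formula.** Age of results at surgery = (S − D) + d. Doses taken after the draw = actual surgery day − D, which is the same number.

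**On schedule (d = 0).** Results are 0-5 days old.

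**Slip of 7 days.** 0 + 7 = 7 up to 5 + 7 = 12 days. For S = 22 moved to Day 29:
- drawn Day 22: 7 days, 7 further doses
- drawn Day 21: 8 days, 8 further doses
- drawn Day 17: 12 days, 12 further doses

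With the preferred timing (D = S or S − 1), the maximum slip gives 7-8 days.

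**Slips of 1-6 days.** 0 + 1 = 1 up to 5 + 6 = 11 days.

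**When do results pass 5 days?** (S − D) + d > 5 requires d ≥ 6 − (S − D).

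| Days from draw to planned surgery | Allowed (S, D) pairs | Smallest slip past 5 days | Slips of 1-7 that pass | Combinations past 5 days |
|---|---|---|---|---|
| 0 | 12 | 6 | 2 | 24 |
| 1 | 12 | 5 | 3 | 36 |
| 2 | 12 | 4 | 4 | 48 |
| 3 | 11 | 3 | 5 | 55 |
| 4 | 10 | 2 | 6 | 60 |
| 5 | 9 | 1 | 7 | 63 |
| Total | 66 | | | 286 of 66 × 7 = 462 |

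With preferred timing, a slip of up to 4 days never passes 5 days, and 24 + 36 = 60 of 24 × 7 = 168 combinations do.

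**Which text governs?** Of the 286, 153 end with surgery on or before Day 22. For those, only the Section 6.2.4 NOTE clearly applies, because footnote k belongs to the Days 22-28 column. The other 133 end after Day 22.

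All counts are of calendar combinations with equal weight. They are not probabilities.

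**The case against.** **The waiver forbids nothing.** It removes a protocol-mandated repeat of what Section 6.2.4 treats as standard pre-operative tests. A surgical team may well re-test before a postponed operation. This stands: the documents do not show local practice, so the finding is about the protocol minimum.

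**The 5-day limit is weak as a safety standard.** Section 6.2.4 calls it logistical, and no section sets a validity period for clinical results. This stands too. The 5 days serve only as a consistency yardstick. A reader might infer from the contrast with research blood that the protocol ranks research above safety. The text does not support that: the research redraw is itself optional, and a paired research sample has its own reason to sit close to surgery.

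**Longer unmonitored stretches exist earlier.** A patient booked for Day 22 and drawn on Day 17-22 takes 16-21 doses before any full panel. That is true, and the extension is not the longest gap. What sets it apart is an explicit release from a pre-operative check that the protocol otherwise ties to the date of surgery.

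**Other safeguards continue.** Glucose, adverse events and medications are reviewed weekly. Section 3.4 lets the investigator stop treatment for a laboratory abnormality, and Section 5.6 requires weekly LFTs after a Grade 2 or higher liver rise. These narrow the gap, but the last two act only once an abnormality is known and cannot find the first one.

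**The calendar.** The clinical-blood-test row of Table 6.1 reads "To be performed between days 9 through 21" and shows nothing under Days 22-28. The adverse-event row looks equally empty there although Section 6.2.3 requires that assessment, so the blank may be an artefact of reading the table. The finding rests on the NOTE and footnote k instead.

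**Conclusion.** The concern holds as a narrow point of safety monitoring, worth considering and inexpensive to fix. For a patient whose surgery slips after the draw, the protocol minimum leaves CBC, chemistries, LFTs and coagulation results 1-12 days old at surgery, with as many further doses, against 0-5 days on schedule. During that time no scheduled test covers a new asymptomatic cytopenia, creatinine rise or liver signal.

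Three stronger readings should be avoided. A reader might infer that any delayed patient has results 7-12 days old; that range needs the full 7-day slip, and 12 days needs the least-preferred draw day as well. A reader might take 286 of 462 as a likelihood; the documents give no distribution of draw days or slips. A reader might infer that patients go into the extension unmonitored or come to harm; weekly glucose and adverse event review continue, and the frequency of a missed change cannot be quantified from the documents.

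The figures assume a single slip of at most 7 days, daily dosing without omission, and no re-testing beyond what the protocol requires. Sample size, power and alpha are unaffected.

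**What to change.** Replace the clinical-blood-test waiver in the Section 6.2.4 NOTE and in footnote k with text such as:

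*If surgery is delayed and the clinical blood results would be more than 5 days old at the new date, repeat CBC with differential, chemistries, LFTs and coagulation studies within 5 days before the new date, with the research redraw or a scheduled glucose draw where possible. Apply Table 5 when results arrive.*

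Mark the conditional repeat under Days 22-28 in Table 6.1. The change to the NOTE matters most, since it also governs slips that end by Day 22. The waivers for history, examination and imaging can stay.

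**Cost.** A short amendment to two passages and one table cell. Patients on schedule need no extra panel. For a single slip, 462 − 286 = 176 of the date combinations need none and 286 need one. If all 20 patients slipped once and all passed 5 days, that would be 20 extra panels. The downside is usually one added panel for a delayed patient, and an added blood draw where it cannot share an existing one. A repeat on Day 11 or later follows 10 scheduled doses, so an omission prompted by it does not by itself make a fully dosed patient non-evaluable under Section 7.
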